6.2 Dose Modifications/Delays

- 6.2.1 Table 6.3 should be adhered to for all toxicities considered at least possibly related to abemaciclib as noted below. If a participant experiences a toxicity unlikely or unrelated to treatment with abemaciclib but may still warrant a hold or reduction of study drug for safety, discussion and approval by Overall Principal Investigator and Study Sponsor, [name] [name] is recommended.
- 6.2.2 When treatment must be held pending resolution of toxicity to grade 1 or return to baseline, and the toxicity is a lab abnormality, in cases where participant had a pre-existing laboratory abnormality at baseline, the toxicity can be considered "resolved" from a hold perspective when it has resolved to within 1 grade of the baseline value. NOTE: For the purposes of data entry, values from screening assessments should be entered in as 'baseline' values. However, true "baseline values" for the purpose of dose modifications on study, etc. will be considered the last assessments/tests performed prior to initiation of study therapy.
 - EXCEPTION: In instances where the value within 1 grade of the baseline value would still require a hold, continue to hold until resolution of toxicity to grade 1 or return to baseline.
- 6.2.3 Participants who experience an adverse event that requires a treatment delay or dose reduction should be monitored with appropriate laboratory testing or other clinical evaluation at least weekly until resolution
- 6.2.4 Following a dose delay which resumes mid cycle, day 1 procedures not associated with the adverse event do not need to be repeated.
- 6.2.5 No more than 2 levels of dose reduction are permitted in this study. Participants cannot be treated below dose level -2. If a participant whose abemaciclib dose has been reduced by 2 dose levels requires another dose reduction, treatment on study must be stopped unless the participant has benefited from the study, in which case the investigator will contact the overall Principal Investigator, [name] [name], to determine if the participant will remain in the study.
- 6.2.6 A treatment delay of up to 28 days is permitted. If the toxicity has not resolved after a 4-week delay, the participant must be removed from study treatment unless the participant has benefited from the study, in which case the investigator may contact the Overall Principal Investigator, [name] [name], to determine if the participant will remain in the study.

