- 6.2.7 Dose re-escalation is never permitted in this study.

- 6.2.8 Cycle length will be 4 weeks (28 days), even if treatment is held for toxicity. There is no stopping in counting cycles/days for those periods where a subject's drug is withheld. All study evaluations and treatments should continue as if study treatment is not being held.
- 6.2.9 If study drug is held across a time point which requires collection of a research blood sample, please contact the Sponsor Coordinating Center or Overall PI ([name] [name]) to confirm whether or not the sample should be collected or if the drug hold will negate the value of collection of the sample in question. If you anticipate the occurrence of such a scenario, please contact the Sponsor Coordinating Center as soon as possible in order to establish a plan prior to the time point in question.
- 6.2.10 Participants whose treatment is interrupted or permanently discontinued due to an adverse event or clinically significant laboratory value, must be followed as outlined in Table 6.3, at least once a week for 4 weeks, and subsequently at 4-week intervals, until resolution or stabilization of the event, whichever comes first. All participants must be followed for adverse events and serious adverse events for 30 days following the last dose of abemaciclib. All SAEs must be reported as detailed in Section 7.4.

Table 6.3: Criteria for dose-modification and re-initiation of abemaciclib treatment

Table 6.3 should be adhered to for all toxicities considered at least possibly related to abemaciclib as noted below. If a participant experiences a toxicity unlikely or unrelated to treatment with abemaciclib but may still warrant a hold or reduction of study drug for safety, discussion and written approval by Overall Principal Investigator and Study Sponsor, [name] [name] is recommended.

Toxicity Actions

(organized per CTCAE v 4.0)

Investigations (for hyperglycemia, see metabolism disorders)

Unless otherwise specified, during duration of toxicity.

General Guidance for Hepatic Monitoring

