Details for hepatic monitoring depend upon the severity and persistence of observed laboratory test abnormalities. If a study patient experiences elevated ALT 5×ULN and elevated TBL 2×ULN, or ALT 8×ULN, liver tests, including ALT, AST, TBL, direct bilirubin, gamma glutamyl transferase (GGT), and creatine phosphokinase (CPK), should be repeated within 3 to 5 days to confirm the abnormality and to determine if it is increasing or decreasing. If the abnormality persists or worsens, clinical and laboratory monitoring should be initiated by the investigator, based on the hepatic monitoring tests below.

Hepatic Hematology Haptoglobin

Hemoglobin

Hematocrit RBC WBC

Neutrophils, segmented and bands

Lymphocytes
Monocytes
Eosinophils
Basophils

Platelets

Hepatic Chemistry

Total bilirubin
Direct bilirubin

Alkaline phosphatase

ALT AST

GGT CPK

Hepatic CoagulationProthrombin Time
Prothrombin Time, INR

Hepatic Serologiesa

Hepatitis A antibody, total Hepatitis A antibody, IgM Hepatitis B surface antigen Hepatitis B surface antibody Hepatitis B Core antibody Hepatitis C antibody Hepatitis E antibody, IgG Hepatitis E antibody, IgM

Anti-nuclear antibody
Anti-actin antibody

Anti-smooth muscle antibody

Abbreviations: ALT = alanine aminotransferase; AST = aspartate aminotransferase; CPK = creatine phosphokinase; GGT = gamma-glutamyl transferase; Ig = immunoglobulin; INR = international normalized ratio; RBC = red blood cells; WBC = white blood cells.

a Reflex/confirmation dependent on regulatory requirements and/or testing availability.

ALT/SGPT or AST/SGOT

- Grade 2 (>3.0- 5.0 x ULN) WITHOUT increase in total bilirubin above 2 x ULN

First Occurrence:

Interrupt until resolution to ≤ grade 1, then

- If resolution to grade ≤1 in ≤ 7 days, resume ABEMACICLIB at the current dose level
- If resolution to ≤ grade 1 takes > 7 days, resume ABEMACICLIB at one lower dose level

Second/Third Occurrence:

Interrupt until resolution to ≤ grade 1, then resume ABEMACICLIB at one lower dose level

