ALT/SGPT or AST/SGOT - Grade 3 (> 5.0 - 20.0 x ULN)	First Occurrence: Interrupt until resolution to ≤ grade 1, then • If resolution to grade ≤1 in ≤ 7 days, resume ABEMACICLIB at the current dose level • If resolution to ≤ grade 1 takes > 7 days, resume ABEMACICLIB at one lower dose level Once resolved to ≤ grade 1, monitor liver function tests every other week or more frequently if clinically indicated until the end of treatment with study medication. Second/Third Occurrence: Interrupt until resolution to ≤ grade 1, then resume ABEMACICLIB at one lower dose level Once resolved to ≤ grade 1, monitor liver function tests every other week or more frequently if clinically indicated until the end of treatment with study medication.
ALT/SGPT or AST/SGOT - Grade 3 (> 5.0 - 20.0 x ULN) WITH increase in total bilirubin above 2 x ULN in the absence of cholestasis	Discontinue abemaciclib.
ALT/SGPT or AST/SGOT - Grade 4 (>20.0 x ULN)	Discontinue abemaciclib.

General Guidance for Increases in Serum Creatinine and Assessment of Renal Insufficiency

Abemaciclib has been shown to increase serum creatinine due to inhibition of renal tubular transporters without affecting glomerular function (as measured by iohexol clearance). In clinical studies, increases in serum creatinine occurred within the first month of abemaciclib dosing, remained elevated but stable through the treatment period, were reversible upon treatment discontinuation, and were not accompanied by changes in markers of renal function, such as blood urea nitrogen (BUN), cystatin C, or calculated glomerular filtration rate based on cystatin C.

Creatinine - Grade 2 (>1.5 - 3 x ULN)	Maintain treatment with ABEMACICLIB
Creatinine - Grade 3 (> 3.0 - 6.0 x ULN) if believed deterioration of renal function is suspected (as evidenced by changes in other markers of renal function, such as BUN, cystatin C, or calculated GFR based on cystatin C).	Interrupt treatment until resolution to ≤ grade 1 or returned to baseline, treatment may resume at the same dose level or a 1 dose level decrease, at the investigator's discretion. Continuation of ABEMACICLIB is permitted upon recovery to stable Grade 2 if the investigator and overall principal investigator ([name] [name]) agree that the event is not considered clinically significant.

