Interstitial lung disease (ILD) / pneumonitis has been identified as an adverse drug reaction for abemaciclib. Adverse events reported included events such as interstitial lung disease, pneumonitis, obliterative bronchiolitis, organizing pneumonia, pulmonary fibrosis. The majority of events were Grade 1 or Grade 2 with serious cases and fatal events reported.

Monitor for clinical symptoms or radiological changes indicative of ILD/pneumonitis and please ask patients to report any new or worsening pulmonary symptoms. Symptoms may include hypoxia, cough, dyspnea, or interstitial infliltrates on radiologic exams.; these symptoms should be investigated and treated as per local clinical practice and/or guidelines (including corticosteroids as appropriate). Infectious, neoplastic, and other causes for such symptoms should be excluded by means of appropriate investigations. Investigations may include imaging such as high resolution computer tomography (HRCT), broncheoalveolar lavage (BAL), and biopsy as clinically indicated (see also Table 7: refer to dose adjustment table for interstitial lung disease/pneumonitis).

Grade 1 or 2	Maintain treatment with ABEMACICLIB		
Persistent or recurrent Grade 2 toxicity that does not resolve with maximal supportive measures within 7 days to baseline or Grade 1	Interrupt until resolution to ≤ grade 1 or baseline, then resume ABEMACICLIB at one lower dose level		
Grade 3 or 4	Discontinue ABEMACICLIB		
Other unspecified RELATED adver	se events		
Other unspecified Grade 1 and 2 events considered at least possibly related to ABEMACICLIB	Maintain treatment with ABEMACICLIB		
Other unspecified persistent or recurrent Grade 2 events	Interrupt until resolution to ≤ grade 1 or baseline, then resume ABEMACICLIB at one lower dose level		

considered at least possibly related to ABEMACICLIB that dose not resolve with maximal supportive measures within 7 days to baseline or Grade 1	
Other unspecified Grade 3 or 4 events considered at least possibly related to ABEMACICLIB	Interrupt treatment until resolution to ≤ grade 1 or baseline, then resume ABEMACICLIB at one lower dose level. Continuation of ABEMACICLIB is permitted upon recovery to stable Grade 2 if the investigator and overall principal investigator ([name] [name]) agree that the event is not considered clinically significant.
Other unspecified UNRELATED ad	verse events

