Other unspecified events of any grade considered unlikely to be related or not related to study drug.	Maintain treatment with ABEMACICLIB. Interruption of ABEMACICLIB is permitted at the treating investigator's discretion. It is recommended that the investigator consults with the overall principal investigator ([name] [name]) to determine that this is in the interest of the participant.

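### Table 6.3 holds drug for ALT/AST grade 2 only when bilirubin is not above 2 x ULN, so the worse liver state gets the laxer written action

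*Combined protocol and SAP*

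**What the plan says.** Table 6.3 in Section 6.2 sets the dose action for related toxicities, and its introduction tells sites: "Table 6.3 should be adhered to for all toxicities considered at least possibly related to abemaciclib as noted below". The opening of Section 6 also sends interruptions for unacceptable toxicity to this table. The relevant entries are:

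- **ALT/AST grade 2:** "Grade 2 (>3.0- 5.0 x ULN) WITHOUT increase in total bilirubin above 2 x ULN". Hold until grade 1 or lower. At first occurrence, restart at the same dose if recovery takes 7 days or less, otherwise one level lower.
- **ALT/AST grade 3, no bilirubin condition:** hold.
- **ALT/AST with bilirubin:** "Grade 3 (> 5.0 - 20.0 x ULN) WITH increase in total bilirubin above 2 x ULN in the absence of cholestasis". Discontinue.
- **ALT/AST grade 4:** discontinue.
- **Residual related row:** "Other unspecified Grade 1 and 2 events considered at least possibly related to ABEMACICLIB". Continue treatment.
- **Second residual row:** persistent or recurrent grade 2 events are held if the event "dose not resolve with maximal supportive measures within 7 days to baseline or Grade 1" (the first word is a slip for does), then restarted one level lower.
- **Residual related grade 3-4 row:** hold, then restart one level lower.

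Bilirubin has no row of its own. The hepatic guidance asks for repeat liver tests within 3 to 5 days, with this trigger: "If a study patient experiences elevated ALT 5×ULN and elevated TBL 2×ULN, or ALT 8×ULN".

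**The concern.** The bilirubin condition in the grade 2 row removes the more worrying state from the hold rule, and no other row takes it up. At grade 3 without cholestasis, the table treats added bilirubin above 2 x ULN as worse: the action moves from hold to discontinue. At grade 2 the same addition moves it from hold to no row, with continued dosing as the only written fallback. The inconsistency is visible inside the table and needs no outside standard.

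The follow-up rules do not make up for this. Section 6.2.3 says: "Participants who experience an adverse event that requires a treatment delay or dose reduction should be monitored with appropriate laboratory testing", at least weekly. Section 6.2.10 applies when drug is interrupted or stopped. A participant who continues meets neither condition. Within the table, discretion to hold is written only for unrelated events: "Interruption of ABEMACICLIB is permitted at the treating" investigator's discretion. What is at stake is participant safety in a rare state. No effect on PFS6 is claimed.

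**Working it through.** The plan gives no figure to reproduce here, so the check is to read the rows against possible states.

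**1. Which states have a row.** Take ALT/AST at 4, 5, 6, 10 and 25 x ULN, bilirubin at 1, 2.5 and 3.5 x ULN, and cholestasis present or absent: 5 x 3 x 2 = 30 states. The states without a row are ALT/AST 4 or 5 with bilirubin 2.5 or 3.5, with or without cholestasis: 2 x 2 x 2 = 8. The other 22 match at least one row. The pattern is:

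| ALT/AST (x ULN) | Bilirubin (x ULN) | Row | Written action |
|---|---|---|---|
| 4 | 1 | grade 2 | hold |
| 4 | 2.5 | none | residual only: continue; hold if not resolved in 7 days |
| 6 | 1 | grade 3 | hold |
| 6 | 2.5, no cholestasis | grade 3 with bilirubin | discontinue |
| 6 | 2.5, cholestasis | grade 3 | hold |
| 25 | any | grade 4 | discontinue |

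The second line is the only one in which a higher bilirubin brings a laxer action. Read as at or above, the repeat-test trigger reaches the gap only at exactly 5 x ULN. It names ALT and not AST.

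**2. How wide the band is.** The protocol grades by CTCAE v4.0 but does not print its bilirubin cut-offs. If bilirubin grade 3 starts above 3 x ULN (assumed), the residual grade 3-4 row would hold drug there, and the continue fallback covers bilirubin from above 2 to 3 x ULN. Without that assumption it could cover all values above 2 x ULN.

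**3. Timing in Cohort 1, the cohort that Section 2.4 describes as still open.** Table 10.1 has one on-drug chemistry, on Day 8 +/- 1, and surgery after 10-14 days of drug. Surgery is counted here as falling on Day 10-14.

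- 7-day test: Day 7, 8 or 9 + 7 = Day 14, 15 or 16, against a latest surgery day of 14.
- Days from draw to surgery: 10 - 9 = 1, up to 14 - 7 = 7.
- Doses at two a day: 2 x 1 = 2, up to 2 x 7 = 14.
- Amount at 300 mg a day: 300 mg, up to 2,100 mg.

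The second residual row can therefore hardly act before surgery, whereas the grade 2 row holds at once. Section 5.2 lets earlier Cohort 1 participants stay on drug under the Cohort 2 calendar. There, after Cycle 1, scheduled chemistries are 28 days apart: 28 x 2 = 56 doses. Their number is not given.

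**4. Frequency.** ALT and AST increases are anticipated (Section 6.1.1), but neither is in the Section 2.2 list of related events at 10% or more of 352 patients. Each is thus below 0.10 x 352 = 35.2 patients, or below 0.10 x 20 = 2.0 participants at the Cohort 1 cap. If 1-10% of these also had bilirubin above 2 x ULN at grade 2 (assumed), the count is below 2.0 x 0.01 = 0.02 to 2.0 x 0.10 = 0.20 participants per enzyme. If ALT and AST rises never overlapped, the bounds double to 0.04 and 0.40.

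**The case against.** The strongest reply is that continued dosing is an inference. The residual rows are for events not specified elsewhere, and ALT/AST has its own rows, so the table may simply be silent. That stands: a reader might infer that the protocol orders dosing to go on, and the text does not go that far. But silence is no better, because the residual row is then still the only written action for a related grade 2 event.

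Other safeguards are real but partial.

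- Bilirubin increase is not among the anticipated toxicities in Section 6.1.1. A related, non-serious grade 2 or 3 rise is therefore unexpected and goes to the Overall PI within 5 calendar days (Section 7.4.3), provided that it counts as an adverse event under Section 7.1.1.1. From a Day 7-9 draw, with notification the same day, that means Day 12-14, which can be after surgery.
- Bilirubin above ULN calls for direct and indirect fractions (Table 10.1, footnote o), and Section 10 allows extra procedures when clinically indicated.
- Section 5.2 relies on standard pre-operative evaluation, which may detect the problem.
- Section 5.5 lets the investigator stop treatment, and many would.

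None of these states a hold for this combination.

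Two further extensions are tempting, and the documents do not support them. One is that the grade 3-4 creatinine rows have the same fault, since they apply only when renal deterioration is suspected. The creatinine guidance in the table covers that case. Even if the residual row were applied, it would be more cautious at grade 3 and would not reverse the order at grade 4. The other is that the gap lets Cohort 1 participants start drug with abnormal liver tests, because Section 5.2 uses Table 6.3 on Day 1. A pre-dose abnormality cannot be drug-related, so the unrelated row and its discretion apply.

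**Conclusion.** The point holds for the liver rows only. ALT/AST of more than 3.0 and up to 5.0 x ULN with bilirubin above 2 x ULN has no row, and its only written fallback is laxer than the action for the same ALT/AST with lower bilirubin. This rests on the rows as printed, on no row being missing between the grade 2 and grade 3 entries, and, for the width of the band, on the assumed bilirubin cut-off of 3 x ULN.

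The practical size is small: well under one expected participant at the Cohort 1 cap under the assumed shares, and up to 14 further doses if the state occurs. It does not show that harm is likely. The case for acting is that a hepatic safety rule is written in the wrong order and is cheap to correct. It is a minor point, worth including in any further amendment.

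**What to change.** Three edits to Table 6.3:

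1. Delete the bilirubin condition from the ALT/AST grade 2 row, so that every grade 2 rise is at least held. This uses the action already in that row.
2. Where bilirubin exceeded 2 x ULN, require bilirubin as well as ALT/AST to return to grade 1 or baseline before restart. Without this, edit 1 would let drug resume at the current dose on ALT/AST recovery alone.
3. Extend the 3 to 5 day repeat-test trigger to ALT or AST above 3 x ULN with bilirubin above 2 x ULN.

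Whether this state should lead to discontinuation is a clinical choice for the sponsor. A hold is the least that fits the table's own order.

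The cost is an occasional extra hold and an unscheduled repeat liver test. Total bilirubin, ALT and AST are already in the chemistry panel, so no scheduled visit or draw is added.

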7. ADVERSE EVENTS: LIST AND REPORTING REQUIREMENTS

Adverse event (AE) monitoring and reporting is a routine part of every clinical trial. The following list of reported and/or potential AEs (Section 7.2) and the characteristics of an observed AE (Section 7.3) will determine whether the event requires expedited reporting in addition to routine reporting in the study specific database.

7.1 General Information and Periods of Observation, Recording and Reporting

Information on all adverse events, whether reported by the participant, directly observed, or detected by physical examination, laboratory test or mother means, will be collected, recorded, followed and reported as described in the following sections.

Adverse events experienced by participants will be collected and recorded from the first dose of study treatment until 30 days after the last dose of study medication. The period for collection and recording of adverse events is extended for participants with ongoing reportable adverse events (protocol section 7.4) at least possibly related to study agent; for such participants, adverse events will be followed until the reportable event has resolved, stabilized, or determined to be irreversible by the reporting investigator. The Coordinating Center should be consulted prior to ending the follow-up of events that have stabilized.

7.1.1 Definitions

7.1.1.1 Adverse Event (AE)

An adverse event (AE) is any undesirable sign, symptom or medical condition or experience that develops or worsens in severity after beginning study treatment, even

if the event is not considered to be related to the study.

Abnormal laboratory values or diagnostic test results constitute adverse events only if they induce clinical signs or symptoms or require treatment or further diagnostic tests.

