Dosages for pediatric and geriatric populations are not known at this time. There is no information for dosage adjustments in patients with renal insufficiency, hepatic insufficiency, or

concomitant disease, or who are undergoing dialysis.

Safety and Efficacy

Validated safety data for 352 patients treated with abemaciclib in Studies JPBA, JPBB, JPBC, JPBH, JPBJ, and JPBN are available. Cumulatively, the most common TEAEs ($\geq 10\%$) possibly related to study drug for patients receiving abemaciclib either as a single agent, with endocrine therapy, or with chemotherapy, are diarrhea (64.2%), nausea (44.3%), fatigue (39.8%), neutropenia (27.0%), vomiting (24.1%), thrombocytopenia (21.3%), leukopenia (21.0%), anemia (17.6%), decreased appetite (17.6%), and blood creatinine increased (14.5%).

The majority of deaths reported for patients in the studies with available safety data were due to study disease.

As of 14 October 2014, 31 patients in Studies JPBA, JPBB, JPBC, JPBE, JPBH, JPBJ, and JPBN experienced 43 SAEs that were reported as possibly related to study drug. SAEs that were possibly related to study drug and experienced by more than 1 patient included diarrhea (5 patients), dehydration (4 patients), neutropenia and pneumonia (3 patients each), and anemia, confusional state, nausea, pyrexia, and sepsis (2 patients each).

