6.1 Anticipated Toxicities

In order for an event to be expected (known correlation to study drug) for the purposes of adverse event reporting, the event must be included in this section.

- 6.1.1 A list of adverse events of all grades suspected to be abemaciclib treatment related according to review of Investigator's Brochure, organized by CTCAE v4.0 category, includes:
 - BLOOD & LYMPHATIC SYSTEM DISORDERS White blood cell decreased, Neutrophil count decreased, Platelet count decreased, Anemia
 - EYE DISORDERS Cataract
 - GASTROINTESTINAL Diarrhea, Nausea, Vomiting, Dry mouth, Stomatitis
 - GENERAL DISORDERS Fatigue
 - INFECTIONS & INFESTATIONS Upper respiratory infection, lung infection, pharyngitis, urinary tract infection, conjunctivitis, sinusitis, vaginal infection, sepsis
 - INVESTIGATIONS Creatinine increased, Weight loss, Aspartate aminotransferase increased, Alanine aminotransferase increased, GGT increased
 - METABOLISM & NUTRITION DISORDERS Anorexia
 - MUSCULOSKELETAL AND CONNECTIVE TISSUE DISORDERS Muscular weakness
 - NERVOUS SYSTEM DISORDERS Dysgeusia, Dizziness
 - RESPIRATORY, THORACIC & MEDIASTINAL DISORDERS Pneumonitis
 - SKIN AND SUBCUTANEOUS TISSUE DISORDERS Alopecia, Rash, Pruritis

• VASCULAR DISORDERS – Thromboembolic event

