7.4.5 Protocol-Specific Expedited Adverse Event Reporting Exclusions

For this protocol only, the AEs/grades listed below do not require expedited reporting to the Overall PI or the DFCI IRB. However, they still must be reported through the routine reporting mechanism (i.e. case report form).

Events **not** considered to be serious adverse events for this protocol are:

- Lymphopenia (grade 2-4)
- Hospitalization for routine treatment or monitoring of the studied indication, not associated with any deterioration in condition, or for elective procedures (including off-treatment hospitalization for re-resection within 30-days of last dose of study drug to treat progressive disease)
- Hospitalization for elective or pre-planned treatment for a pre-existing condition that did not worsen since beginning study drug
- Emergency outpatient treatment for an event not fulfilling the serious criteria outlined above and not resulting in inpatient admission
- Hospitalization for seizure, related to GBM (disease under study) and unlikely/unrelated to study treatment

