3.10 Safety Assessments and Toxicity Monitoring

The study teams at all participating institutions are responsible for protecting the safety, rights and well-being of study participants. Recording and reporting of adverse events that occur during the course of a study help ensure the continuing safety of study participants.

All participants receiving investigational agents will be evaluated for safety. The safety parameters include all laboratory tests and hematological abnormalities, physical examination findings, and spontaneous reports of adverse events reported by participants. All toxicities encountered during the study will be evaluated according to the NCI criteria specified in the protocol. Life-threatening toxicities must be reported immediately to the DF/HCC Sponsor via the Coordinating Center and IRB, both DFCI and local as applicable.

Additional safety assessments and toxicity monitoring will be outlined in the protocol.

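### The adverse event definition omits laboratory abnormalities that are asymptomatic, untreated and not retested, so AE-based laboratory toxicity rates are biased low

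*Combined protocol and SAP*

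**What the plan says.** Section 7.1.1.1 states: "Abnormal laboratory values or diagnostic test results constitute adverse events only if they induce clinical signs or symptoms or require treatment or further diagnostic tests". That gives three alternative routes to AE status: symptoms or signs, treatment, or more testing. Severity grade and a change in dosing are not among them.

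Other parts of the protocol handle laboratory findings differently:

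- Section 6.1.1 lists "White blood cell decreased, Neutrophil count decreased, Platelet count decreased, Anemia" together with creatinine, AST, ALT and GGT increases, and presents the list as covering adverse events at every grade.
- Section 7.4.5 excuses grade 2 to 4 lymphopenia from expedited reporting but keeps it on the case report form.
- Section 6.2.10 requires follow-up when drug is interrupted or stopped "due to an adverse event or clinically significant laboratory value", which sets the two apart.
- Appendix B 3.10 says: "The safety parameters include all laboratory tests and hematological abnormalities". It also has toxicities evaluated by the NCI criteria.

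On data and analysis, section 7.7 sends AEs to the toxicity forms and the form list in section 12.1.2 names no laboratory form. Section 13.4 promises descriptive safety statistics without mentioning graded laboratory data. Safety is a secondary objective of both cohorts (section 1.3).

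**The concern.** If the toxicity form is the only route into the safety summary, the AE definition decides which laboratory toxicity is reported. A definition that ignores grade will drop findings that CTCAE would grade and that section 6.1.1 expects to see. The third route is also undefined: one site may treat a repeat blood count as a further diagnostic test and another may not. In a multi-center study the same laboratory value could then be counted at one site and not at another. What is at stake is the reported result of a secondary objective. The primary endpoints are unaffected.

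**Working it through.** The documents state no figure on this point, so there is nothing to reproduce. The check sets the provisions side by side.

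**1. What the definition leaves out.** Take findings that cause no symptoms and need no treatment.

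| Finding | What Table 6.3 does | AE under 7.1.1.1? |
|---|---|---|
| Grade 1-2 neutropenia, thrombocytopenia or anemia | No cytopenia row below grade 3 | No, unless retested |
| Grade 2 creatinine | Treatment maintained | No, unless retested |
| Grade 1 ALT or AST | No row | No, unless retested |
| Related grade 2-3 ALT or AST; related grade 3-4 neutropenia or thrombocytopenia | Interruption until recovery to a stated grade | Only if a retest counts as further testing |

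The first three rows are a clear loss. The fourth depends on how the definition is read.

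**2. Does a retest count?** Hematology and chemistry are scheduled on Days 1 and 8 before surgery in Cohort 1. In Cohort 2 they fall on Days 1 and 15 of cycle 1, Day 1 of later cycles and end of treatment (section 10). Section 6.2.10 asks for follow-up at least weekly for 4 weeks after an interruption, which is denser than that schedule. Recovery to a given grade cannot be shown without a new result. On a natural reading, then, interrupting values do require further tests.

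The text does not settle it, for three reasons:

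- Section 6.2.3 ties weekly testing to a participant who already has an adverse event, so it cannot be used to confer that status.
- Section 6.2.10 names laboratory values as an alternative to adverse events.
- The 3-to-5-day liver retest starts at ALT 8 x ULN, or at 5 x ULN with bilirubin 2 x ULN. An isolated ALT between 5 and 8 x ULN is grade 3 but does not trigger it.

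**3. Scale.** Section 2.2 gives related-event rates from 352 participants. Applied to the 32 planned in Cohort 2:

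- neutropenia: 32 x 0.270 = 8.6
- thrombocytopenia: 32 x 0.213 = 6.8
- leukopenia: 32 x 0.210 = 6.7
- anemia: 32 x 0.176 = 5.6
- raised creatinine: 32 x 0.145 = 4.6

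If a share f of neutropenia cases is asymptomatic, untreated and not retested, the expected loss is 8.6 x f. The documents give no value of f, so the loss could be anywhere from none to all 8.6. These counts also assume that the section 2.2 rates carry over, although they pool single-agent and combination use.

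**4. Expedited reporting.** Section 7.4.2 is worded for medical events equivalent to the listed grades, while the table in section 7.4.3 is built on AE characteristics. Amylase and lipase are measured in both cohorts but are absent from section 6.1.1, so they are unexpected. An at least possibly related grade 4 value falls under the Table 6.3 row for other unspecified events. That leads to interruption and so to section 6.2.10 follow-up. A grade 4 value judged unrelated, with drug continued and no retest, is within 7.4.2 on one reading and outside the 7.4.3 table on another.

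**The case against.** The strongest reply is that the third route does most of the work. Values that interrupt drug carry mandatory weekly follow-up and cannot be shown to have recovered without a retest, so most would qualify as AEs. This stands, and it confines the clear loss to findings that prompt no action.

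A reader might infer that dose-stopping or unexpected grade 4 values need never be reported. The documents do not support that. All dose changes must be recorded (section 5.1) and the reason for leaving therapy goes on the CRF (section 5.5). Monitors compare recorded results with the AE log and check that holds and reductions are justified (Appendix B 5.1). Section 7.4.2 reaches most unexpected grade 4 values. Appendix B 3.10 sends life-threatening toxicities to the sponsor at once, and the Appendix C coversheet labels grade 4 as life-threatening. These records do not by themselves put a value into a toxicity rate, but they do mean that it is not lost.

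It can also be said that section 6.1.1 is a list of terms for judging expectedness, and that Appendix B 3.10 concerns safety parameters and not AEs. Both are fair readings. They soften the conflict but supply no laboratory analysis to fill the gap.

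**Conclusion.** The point holds in limited form. Section 7.1.1.1 is out of step with sections 6.1.1, 6.2.10 and 7.4.5 and Appendix B 3.10, and no planned laboratory summary makes up for it. An AE-based summary will under-count asymptomatic, untreated, unretested abnormalities, mainly low-grade cytopenias, creatinine and transaminase changes. Whether dose-interrupting values count depends on a site's reading. The direction of bias is clear if the rule is followed as written; its size cannot be derived.

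Two further inferences go too far. The drug's most common toxicities are not affected: diarrhea (64.2%), nausea (44.3%) and fatigue (39.8%) lead the list in section 2.2 and are not laboratory findings. Nor can it be shown that the rates here would not be comparable with those in section 2.2, because the documents do not say how the earlier studies defined laboratory AEs. Comparability is simply not established. In expedited reporting, what remains is the ambiguity between sections 7.4.2 and 7.4.3.

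**What to change.** 1. In section 7.1.1.1, add that a laboratory abnormality is also an AE if it is CTCAE grade 3 or higher, or if it leads to a hold, reduction or discontinuation of study drug. The grade 3 threshold is a reviewer's choice; the documents do not dictate one.
2. Bring sections 6.1.1, 6.2.10, 7.4.2, 7.4.3 and 7.4.5 and Appendix B 3.10 into line with that sentence. Say whether 6.1.1 is only a list of terms, how grade 2 lymphopenia is to be treated, and whether 7.4.3 covers every event described in 7.4.2.
3. In section 13.4, add a table of worst post-baseline CTCAE grade and shift from baseline for the scheduled laboratory tests in both cohorts, independent of AE status. Name the baseline, because section 6.2.2 uses screening values for data entry and the last pre-treatment values for dose modification. This table recovers the grade 1-2 findings that the new sentence would still leave out.

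The cost is somewhat more AE forms, one extra table and less favourable reported laboratory toxicity. Some data entry may be needed, since section 12.1.2 lists no laboratory form; the sponsor should confirm what is already in the database. Cohort 2 accrual is complete (section 2.4), so the table is the main gain there. The definition change mainly affects the remaining Cohort 1 participants.
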